Title: Novel Blood Test to Predict Safe Foods for Infants and Toddlers With Food Protein-induced Enterocolitis Syndrome (FPIES)

PI: [name] [name]

NCT: NCT04644783

IRB Protocol Version Approval Date: 9/3/2020

1 **A NOVEL BLOOD TEST TO PREDICT SAFE (NON-TRIGGER) FOODS FOR INFANTS AND TODDLERS**
2 **WITH FOOD PROTEIN-INDUCED ENTEROCOLITIS SYNDROME (FPIES).**

3
4 **PRINCIPAL INVESTIGATOR:** [name] PhD. Research Assistant Professor, Division of
5 Gastroenterology, Department of Internal Medicine, University of Michigan.
6

7 **CO-INVESTIGATORS:**

- 8 *i)* [name] MD. Professor of Internal Medicine, Associate Professor of Pediatrics and Research
9 Associate Professor of Mary H Weiser Food Allergy Center, Medical School, University of Michigan.
10 *ii)* [name] MD. Assistant Professor of Internal Medicine, Division of Allergy and Immunology.
11 *iii)* [name] MD. Associate Professor, Division of Gastroenterology, Department of Internal Medicine,
12 University of Michigan.

13
14 **VERSION 2; ***.**
15
16

17 **I. PROTECTION OF HUMAN SUBJECTS**
18

19 **1. Risks to Human Subjects**
20

21 **A. Human Subjects Involvement, Characteristics, and Design**
22

23 Describe and justify proposed human involvement
24

25 The **objective** of this project is to validate a blood test that can distinguish safe from trigger foods for
26 protein-induced enterocolitis syndrome (FPIES).
27

28 **Background:** FPIES is an allergic disease that leads to repetitive profuse vomiting in response to solid food.
29 In severe cases, when patients fail to thrive, FPIES requires nasogastric tube installment or total parenteral
30 nutrition (TPN). The major challenge in managing FPIES is the identification of safe (non-trigger) foods in a
31 timely manner, while avoiding repetitive allergic reactions and recovery periods. This study proposes a
32 solution to the problem by developing a new blood assay that screens a large number of foods (more than
33 20) in a culture plate. Its purpose is to rapidly predict what the safe foods are. The outcome will overcome
34 the time-lapse required to identify such safe foods, which could normally extend past a year or longer, by
35 which time the child may have failed to thrive or developed food aversions due to association with negative
36 experiences.
37

38 FPIES leads to repetitive hospital and ER visits with 2,064 encounters occurring at the University of

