39 Michigan Health System (UMHS) in the past year (from 11/01/17 until 11/01/18; data obtained using
40 Datadirect for cohort discovery results; FPIES ICD10 K52.2). The latter number of encounters only
41 comprises newly diagnosed patients.
42

43 In this study, FPIES patients will be recruited from the UMHS patient cohort. From 11/01/17 – 11/01/18, this
44 cohort comprised 223 newly diagnosed patients at UMHS. Two sub-groups will be identified as follows: *i)*
45 children exhibiting FPIES reactions to 2-3 foods, *ii)* children exhibiting FPIES reactions to 4 or more foods.
46 The reason for separating patients into these two groups is due the existence of two separate groups [one
47 with 2-3 food triggers, and another with more than 4 food triggers] as previously described by the UMHS
48 Allergists who care for FPIES patients (Volertas S., Hudson E., McMorris G., and [name]. *Annals of*
49 *Allergy, Asthma & Immunology* 121:S119 2018).

50
51 The plan is to enroll up to 20 patients with FPIES: up to 10 exhibiting reactions to 2-3 foods, and up to 10
52 exhibiting FPIES reactions to 4 or more foods. Recruitment will take place at the University of Michigan
53 Allergy Clinics, and University of Michigan Pediatric outpatient clinics.
54

55 **Hypotheses:**

- 56 1. Our blood test that we developed will distinguish safe from trigger foods for FPIES patients.
57 2. The mechanism of FPIES involves innate immunity and the identified heatmap pattern for trigger foods
58 will remain after foods are tolerated.

59 **Specific aims:**

- 60 1. Assess the assay's precision by its predictive accuracy in distinguishing safe foods from trigger foods.
61 2. Evaluate the reliability of the test when using a panel of standardized, frozen foods vs freshly prepared
62 foods
63 3. Demonstrate persistence of the immune reaction to trigger foods by comparing results of the test after
64 trigger foods are tolerated to the initial results

65 **Exploratory aim:**

- 66 1. Gain further insight into the pathophysiology of FPIES through single cell RNASeq

67 **Statistical Design:** A random-effects logit model will be used to model the binary outcome (safe or trigger
68 food) as a function of the 9 biomarker measurements in the assay. The random effect in the logit model will
69 take into consideration of the correlated data measured within the same subject. A cluster Receiver

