70 operating characteristic (ROC) curve analysis will be used to assess the precision of the assay. Specifically,
71 we will compute the area under the cluster ROC curve (AUC), along with a 95% confidence interval (CI).
72 The assay is predictive if the lower limit of the 95% CI is above 0.5, which is the null value indicating no
73 predictive ability.

74 **Brief description of the proposed study**

75 FPIES is a severe food allergy to a wide variety of foods in babies and toddlers. Usually, the symptoms
76 resolve between the ages of 3 to 5 years old. However, the children are at risk of failing to thrive, and
77 requiring a nasogastric tube or TPN. The objective of the study is to validate a newly developed blood assay
78 that will rapidly predict safe (non-trigger) foods for the affected children. In our preliminary data (Case Study
79 HUM00155216), the blood assay safely predicted more than 10 consecutive safe foods without triggering
80 an allergic response. Prior to the assay, allergic reactions and ER visits were repeatedly occurring.

81 **Subject Recruitment:** Subjects will be recruited through the University of Michigan Allergy Clinics, and
82 University of Michigan Pediatric outpatient clinics:

- 83 1. Patients may be referred by the clinician caring for the patient.
- 84 2. Pre-screening by reviewing FPIES visits in the past 2 years will be performed. Data Direct, EMERSE
85 and billing codes may be used to identify potential subjects. The patient's primary allergist or
86 pediatrician will be informed about study team's contact with the identified patients.
 - 87 o Patients will then be contacted by email and/or telephone by the clinical members of the
88 study team to explain the study and determine whether they are interested in participating.
89 Opt out information will be provided in the email and by phone contact.
- 90 3. Patients may self-refer:
 - 91 o The study will be listed in UMHealthResearch.org
 - 92 o Flyers describing the study, with study team contact information, will be posted in the
93 participating clinics.

94 **Inclusion Criteria:**

- 95 1. Patients aged 1 month – 7 years old with a physician diagnosis of FPIES:
 - 96 a. Group 1: Documented reactions to 2-3 trigger foods with recurrent delayed vomiting.
 - 97 b. Group 2: Documented reactions to 4 or more trigger foods with recurrent delayed vomiting.

98 **Exclusion Criteria:**

- 99 1. Patients without a physician diagnosis of FPIES.

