143 b. During that time, food introduction will continue as directed by primary allergist and/or
144 nutritionist
145 9. Blood will be analyzed by the PI in a research lab at the University of Michigan to determine
146 differences in the PI's assay between potentially tolerated and not tolerated foods (see description of
147 laboratory test lines 216-232)
148 10. After identification of potentially "safe foods" to be introduced in the future, the information will be
149 given to the clinical study team and child's clinician, who will contact parents by phone or email
150 (parental preference).
151 a. Parents will be asked to detail current nutritional status, including foods tolerated or not
152 tolerated since the initial blood draw. Results will be recorded by the study team and the
153 parents will be asked to return Questionnaire Two.
154 b. After discussion within the clinical team (including clinical research team and child's
155 clinicians), parents will be instructed to introduce new foods identified as potentially safe into
156 the diet, one at a time for seven days.
157 c. Results of these trials will be recorded on Questionnaire Three and returned to the study
158 team 3 month intervals.

159 11. A second blood draw will be performed, at least 2 weeks after the initial blood draw. 6 cc will be
160 drawn:

- 161 a. To explore the consistency of a standard panel of foods vs individually prepared foods
- 162 b. To perform additional analyses including single cell RNASeq (scRNA-seq) on WBCs
- 163 following treatment with foods.

164 12. Subjects will be followed at 3 month intervals with review of tolerated foods, number and types of
165 known triggers assessed. When a subject is tolerating two or more triggers foods for 3 or more
166 months:

- 167 a. Questionnaire Four will be given to fill out and return
- 168 b. Subject will have 6 mL drawn for analysis
 - 169 i. 5.5 mL to rerun the initial assays
 - 170 ii. 0.5 mL for RNASeq on WBCs following treatment with foods.

171 Study Grid

	Baseline visit - Day 0	Lab Day 0- 14	Lab >2 weeks after initial blood draw	At home 1-3 months	3 up to 36 months	At home every 3 months up to 36 months	> 2 trigger foods tolerated
Consent	X						
Questionnaire 1	X						
Blood Draw		X	x				X
Phone/email/in-person to inform of potentially tolerated foods.				X			
Questionnaire 2				X			
Testing Foods Found as tolerable					X		
Questionnaire 3						X	
Questionnaire 4						X	X

172
173 B. Sources of Materials

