174 The research material obtained from the human subjects

175 1. 6ml of blood in a K2 EDTA (lavender top) blood tube withdrawn by specialized phlebotomists in
176 the blood draw unit (0.5 ml of this will be used to isolate DNA for potential future sequencing under a
177 separate IRB). White blood cells (WBCs) will be isolated from 5.5 ml of blood using ACK buffer lysis of red
178 blood cells, within 1 hour of blood collection, as performed previously for the Case Study (HUM00155216).
179 Blood will be kept on ice in the K2 EDTA tubes during the waiting period (< 1 hour). WBCs will be plated in
180 24 well plates, and exposed to different food homogenates for 3 hours. Total RNA will be extracted, and RT-
181 qPCR for our gene panel will be used to generate the heatmap.

182 A second blood draw may be requested from a limited number of patients, at least 2-4 weeks after
183 the initial blood draw, for scRNA-seq. In this case, the blood will be prepared in the same manner as for the
184 initial draw above, but instead of extracting RNA, samples will be submitted to the UofM Advanced
185 Genomics Core for them to perform scRNA-seq on the samples. The data will be analyzed using the cloupe
186 software by 10x Genomics.

187 A third blood draw may occur (or second blood draw if scRNA were not performed for that patient)
188 after the patient recovers from several triggers. The patient will be screened at 3 month intervals, so the
189 third (or second if no scRNA-seq) will be performed for this purpose at least 3 months after the initial blood
190 draw. In this case, the cells will be prepared in the same manner as the initial blood draw, but treated with
191

193 only a limited number of safe, trigger foods, and outgrown trigger foods.

194 2. At the termination of the protocol samples and data will cease to be accessed, or otherwise
195 accessed again after IRB approval transferred to another existing protocol. There are no plans to destroy
196 records or samples.

197 **Protection of Information:**

198 All data will be kept on REDCap, a password-protected, HIPAA compliant, web-based application
199 developed by Vanderbilt University to capture data for clinical research and create databases and projects.
200 The databases use instruments such as surveys and forms as research capture tools. Projects are self-
201 sufficient and secure databases that can be used for normal data entry or for surveys across multiple

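### The success rule fixes neither held-out scoring, nor the score, nor the pairs compared: scored in-sample, nine noise markers usually pass, and an all-pairs AUC need not show discrimination within a child

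*Combined protocol and SAP*

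**What the plan says.** The statistical plan is one paragraph, under Statistical Design in section I.1.A. The status of each food is modelled by a random-effects logit "as a function of the 9 biomarker measurements in the assay", with a random effect meant to "take into consideration of the correlated data measured within the same subject". For the ROC step, "we will compute the area under the cluster ROC curve (AUC), along with a 95% confidence interval (CI"). The verdict is a single rule: "The assay is predictive if the lower limit of the 95% CI is above 0.5".

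The paragraph does not say that the model's prediction is the quantity ranked in the ROC curve, whether that prediction contains the child's random effect, whether children are scored by a model fitted without them, or whether a trigger food is compared with safe foods of the same child or of all children. No within-child measure of accuracy is planned, and there is no power calculation or target AUC.

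Three other places bear on the point:

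- Enrolment is "up to 20 patients with FPIES: up to 10 exhibiting reactions to 2-3 foods, and up to 10" with four or more triggers.
- The Background describes "developing a new blood assay that screens a large number of foods (more than" 20), and under Sources of Materials the cells go into "24 well plates, and exposed to different food homogenates for 3 hours". These give the number of foods screened. The number per child whose true status is known is not given.
- Study Design item 10b gives the use of the result: "parents will be instructed to introduce new foods identified as potentially safe into" that child's diet.

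**The concern.** The rule alone decides whether the assay is called predictive, so anything that pushes the AUC above 0.5 for another reason matters. There are two such routes.

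The first is optimism. Nine coefficients estimated on up to 20 children, then judged on the same children, will separate their foods to some degree even when the markers carry no information.

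The second is the choice of pairs. A family needs to know which foods are safe for its own child, so the relevant comparison is between foods of one child. If triggers are compared with safe foods across all children, most of the AUC comes from different children, and a score that merely separates many-trigger from few-trigger children can look accurate. A random effect or a clustered variance deals with correlation in the standard error. Neither turns an all-pairs AUC into a within-child one.

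**Working it through.** The plan has no figure of its own to reproduce.

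**Inputs from the documents:** 10 + 10 children (the maximum), 2-3 triggers in one group and 4 or more in the other, nine markers, success if the lower 95% limit exceeds 0.5 (nominal one-sided error 2.5%).

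**Assumptions:** labelled foods per child (20, varied to 10 and to unequal numbers); 4-6 triggers in the upper group (varied to 4-8 and 4-10); intraclass correlation (ICC) of a marker within child 0.3; group shift in a marker of 0 to 1 total SD. One total SD is 1/√0.3 = 1.8 between-child SDs, and half a total SD is 0.9. Noise means a true within-child AUC of 0.5.

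**1. In-sample scoring.** Nine noise markers, 20 labelled foods, no shift, 600 runs: the rule is met in 90% of runs on all pairs and 75% on same-child pairs. Across repeat simulations the second figure is about 65-80%. With a random-intercept fit and a clustered-data variance, the all-pairs figure is 86-91%, with a mean AUC of about 0.60. With leave-one-child-out scores the mean AUC falls to 0.496 (all pairs) and 0.501 (same child), and the rule is met in 9.2% of runs on each.

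**2. Share of same-child pairs.** With means of 2.5 and 5 triggers out of 20:

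- Triggers: 10 × (2.5 + 5) = 75. Safe foods: 10 × (17.5 + 15) = 325.
- All pairs: 75 × 325 = 24,375.
- Same-child pairs: 10 × (2.5 × 17.5 + 5 × 15) = 1,187.5, or 4.9% (4.4-5.6% over the other scenarios).

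**3. A score that knows only the group.** With t triggers and s safe foods per child, AUC = 0.5 + 0.5 × [t₂/(t₁+t₂) − s₂/(s₁+s₂)].

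- 2.5/17.5 against 5/15: 0.5 + 0.5 × (0.667 − 0.462) = 0.603.
- 2.5/7.5 against 5/15 (equal shares): 0.5 + 0.5 × (0.667 − 0.667) = 0.500.
- 2.5/17.5 against 5/10: 0.5 + 0.5 × (0.667 − 0.364) = 0.652.

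The within-child AUC of such a score is exactly 0.5. This illustrates the mechanism; it does not predict what the markers do.

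**4. Locked score, no food-level signal** (2,000 runs per cell, bootstrap of children). Runs in which the all-pairs rule is met:

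| Group shift (total SD) | 0 | 0.25 | 0.5 | 1 |
|---|---|---|---|---|
| 20 foods each | 4.0% | 7.7% | 15.6% | 37.7% |
| 10 foods each | 3.4% | 8.2% | 16.7% | 44.3% |
| 10 safe foods per child with 4+ triggers | 3.7% | 9.9% | 21.5% | 56.2% |
| Equal shares | 4.0% | 4.0% | 4.3% | 4.2% |

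The within-child rule is met in 3-5% of runs throughout.

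**5. Held-out nine-marker score.** With one noise marker shifted by 1 SD, the all-pairs rule is met in about 10-19% of runs and the within-child rule in 7-10%. With no shift, both are about 9-10%.

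**6. Random effect in the score.** The maximum-likelihood random-effect SD is essentially zero at 4-6 triggers, so nothing changes. At 4-8 and 4-10 triggers, adding the predicted random effect moves the in-sample all-pairs AUC of noise from 0.604 to 0.636 and 0.701. The within-child AUC does not move.

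**The case against.** The case for leaving the plan alone has real force on the choice of pairs. The text nowhere says that all pairs are used; if the cluster AUC was meant as same-child pairs, that problem disappears. Hypothesis 1 and Aim 1 ask whether the test separates safe from trigger foods in FPIES patients, and for one cut-off applied to every child the all-pairs AUC is the relevant measure. A 1-SD shift is a strong assumption, and for a held-out score the excess is modest even then. All of this stands, and it is why the second consequence is stated conditionally.

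A reader might infer more: that enrolling by trigger count makes a false success likely, or that an all-pairs AUC is always inflated. The documents do not support either. They show no marker that tracks trigger share, and they do not fix the labelled foods, so shares could be equal. Child-level differences unrelated to share push the other way: a true within-child AUC of 0.80 gives an all-pairs AUC of 0.760 at ICC 0.3 and 0.727 at ICC 0.5.

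A reader might also infer that in-sample scoring is planned. The text is silent. Study Design item 10 returns predicted safe foods to families during follow-up, which implies that some reading rule is in use before the final model is fitted. But the Statistical Design does not name such a rule as the score; it names a model to be fitted and no step that separates fitting from scoring. The food trials in item 10 are useful prospective evidence, but no analysis of them is specified and they do not test predicted triggers.

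**Conclusion.** The concern holds in two parts of unequal weight. The larger is in-sample scoring: if the nine-marker model is judged on the children it was fitted to, a useless assay meets the rule in about 90% of runs, and changing the pairs alone leaves about 65-80%. The smaller is the choice of pairs: it adds false success only if a marker tracks trigger share, or if the predicted random effect enters the score and shares vary widely. For a score without the random effect, the choice of pairs adds nothing when there is no shift or when shares are equal. All sizes rest on assumed labelled foods, trigger counts, ICC and shifts. That the plan leaves score, held-out step and pairs undefined rests on no assumption.

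**What to change.** In the Statistical Design:

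1. Define the score as the marker part of the model, without the predicted random effect, held out by child (for example leave-one-child-out).
2. Add a within-child AUC from same-child trigger-safe pairs, with a 95% CI from resampling children. Base any claim that the assay identifies a child's own safe foods on its lower limit exceeding 0.5.
3. Keep the all-pairs cluster AUC of the same held-out score for any claim about one common cut-off.
4. Report a p-value from shuffling labels within each child and refitting, as a supporting check.

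Item 4 is useful because the CI treats held-out scores as fixed, so noise still passes in about 7-10% of runs, against 2.5-3.3% for the permutation test at a one-sided 0.025. It should not be a second mandatory gate: at 10 labelled foods, requiring both is met in only 85% of runs at a true within-child AUC of 0.70 and 46% at 0.65.

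The cost is a few sentences and some code, with no new data, since each child's assay results, triggers and tolerated foods are already to be recorded (Protection of Information). The CI is slightly wider (SE 0.039 against 0.036 for all pairs at 20 labelled foods), and results will look less favourable than in-sample ones. At a true within-child AUC of 0.70, the held-out within-child CI rule is met in about 98-99% of runs with 20 labelled foods and 94% with 10. At 0.65 the figures are about 83% and 66%, so a weak signal with few labelled foods would be missed in about a third of trials.

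### The Aim 1 success rule tests a clustered AUC against 0.5 without naming the score or the labelled foods; if the nine-biomarker model is scored on the children it was fitted to, a useless assay passes in roughly 83–94% of trials

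*Combined protocol and SAP*

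**What the plan says.** Section I.1.A, Statistical Design, holds the whole statistical plan. The model takes the binary outcome (safe or trigger "food) as a function of the 9 biomarker measurements in the assay. The random effect in the logit model will" allow for correlation within a child. A cluster ROC analysis follows directly: "we will compute the area under the cluster ROC curve (AUC), along with a 95% confidence interval (CI"). The decision rule is then: "The assay is predictive if the lower limit of the 95% CI is above 0.5, which is the null value indicating no" predictive ability. This is the only rule given for Specific Aim 1, which is to assess the assay's "precision by its predictive accuracy in distinguishing safe foods from trigger foods".

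The cohort is small: "The plan is to enroll up to 20 patients with FPIES: up to 10 exhibiting reactions to 2-3 foods, and up to 10" with reactions to four or more. No training and validation split, cross-validation, optimism correction or sample-size justification appears.

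Other passages suggest that a finished test exists. Hypothesis 1 reads "Our blood test that we developed will distinguish safe from trigger foods for FPIES patients", and the brief description says "The objective of the study is to validate a newly developed blood assay". In Study Design step 10 the laboratory result comes first, and then "parents will be instructed to introduce new foods identified as potentially safe into" the diet. No formula, coefficients or cut-off for reading the heatmap is given, and nothing links that reading to the ROC curve.

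**The concern.** Two things that determine what the AUC means are left open.

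**The score.** The logit is the only stated way of combining nine biomarkers into one number. If its fitted values are ranked on the children that produced them, the model has already adapted to chance differences between their safe and trigger foods. Its AUC is expected to exceed 0.5 even for pure noise. The random effect and the clustered interval deal with correlation within a child, not with this upward shift.

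**The labels.** The plan does not say whether the ROC uses only foods of known status at the blood draw or also foods tried later. Step 10 has parents try foods that the assay calls potentially safe, and no step there has them try foods that it flags. If the later outcomes count, newly labelled foods all carry favourable scores while most triggers come from history. That raises the AUC without any predictive ability, even for a locked score.

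Meeting the rule could then say almost nothing about the assay. Because the text settles neither point, both choices could be made after the data are seen.

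**Working it through.** **Inputs from the documents.** Nine biomarkers; up to 20 children, up to 10 with 2–3 triggers and up to 10 with 4 or more; more than 20 foods screened (Background); 24-well plates (Sources of Materials); success if the lower 95% limit exceeds 0.5, which is nominally 2.5% one-sided. The plan states no error rate or power, so there is no figure to reproduce.

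**Assumed, because not given.** 8–40 labelled foods per child; group 2 maximum of 4 to 10 triggers; within-child biomarker correlation 0–0.6; 10–20 children.

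**1. Hand check of in-sample scoring under the null.** Take 20 children × 20 foods with 4–7 triggers in group 2. Triggers m = 10×2.5 + 10×5.5 = 80; safe foods n = 400 − 80 = 320.
- For p unrelated biomarkers the fitted squared separation D² averages about p(1/m + 1/n) = 9(1/80 + 1/320) = 0.141.
- AUC ≈ Φ(√(D²/2)) = Φ(0.265) = 0.605. Simulation gave 0.602.
- With 10 children (m = 40, n = 160), D² = 0.281 and AUC ≈ Φ(0.375) = 0.646. Simulation gave 0.647.
- The null SE is √((m+n+1)/(12mn)) = √(401/307,200) = 0.0361, so passing needs AUC > 0.5 + 1.96×0.0361 = 0.571.
- That means D² > 2×0.1784² = 0.0637, since Φ⁻¹(0.571) = 0.1784. D²·mn/(m+n) is roughly χ² with 9 df, and mn/(m+n) = 64. So P(pass) ≈ P(χ²₉ > 64×0.0637 = 4.08) = 0.91.
- For general m and n the threshold is about 1.96²×π/3 = 4.02. The pass rate therefore depends on the number of biomarkers and hardly on sample size, so more children or foods would not cure it.

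**2. Simulation of in-sample scoring** (clustered variance, rule AUC − 1.96·SE > 0.5).

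| Score | Mean null AUC | Rule met |
|---|---|---|
| Fitted model, fixed effects, same children | 0.60–0.67 | 83–94% |
| Fitted model including the child's random effect | 0.60–0.70 | 88–100% |
| Locked score, labels independent of the assay | 0.50 | 2–5% |

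Other intervals for the in-sample score change little: logit-scale 87–88%, t(19) about 85%, child-level bootstrap 87–89%.

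**3. Locked noise score when the assay selects the foods.** Assume 20 children, 2–3 or 4–6 baseline triggers (mean 3.75 per child), 5 known-safe and 10 unknown foods, 10% of the unknown foods being triggers, and the best-scoring 5 introduced.
- Each child gains 4.5 safe foods and 0.5 triggers. Introduced foods are 4.5/9.5 = 0.474 of safe foods and 0.5/4.25 = 0.118 of triggers.
- The mean rank of the top 5 of 10 is 8/11 = 0.727, so AUC ≈ 0.5 + 0.227×(0.474 − 0.118) = 0.581.
- With m = 85 and n = 190, SE ≈ √(276/193,800) = 0.0377. The shift is 0.081/0.0377 = 2.14 SE, so P(pass) ≈ P(Z > 1.96 − 2.14) = 0.57. Simulation gave 58%.
- Across 5–12 known-safe foods, 4–10 unknown foods, 10–30% triggers among them and 50–75% introduced, the rule was met in about 3–58% of trials. With no selection it was about 3–4%.

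**4. Leave-one-child-out scoring under the null.** The ordinary clustered interval gave 4–11% across separate simulations. A within-child permutation null gave 1.5–3.4% (79 permutations, plain logit).

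**5. Power of that permutation test** (199 permutations, 3 of 9 biomarkers informative, 4–6 triggers in group 2).

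| Children × foods | AUC 0.65 | AUC 0.70 | AUC 0.75 |
|---|---|---|---|
| 20 × 20 | 77% | 98% | 100% |
| 20 × 10 | 52% | 89% | 100% |
| 10 × 20 | 37% | 67% | 89% |
| 10 × 10 | 24% | 52% | 73% |

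**The case against.** The strongest reply is that this is a validation study. The hypotheses and brief description speak of a test already developed, a case study preceded it, and the laboratory must name safe foods before any model on this cohort could be complete. A locked reading may therefore exist, and for it 0.5 would be a sound null. A single marker could also be meant.

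Part of this stands. A reader might infer that the plan commits to in-sample scoring and so has a false-positive rate above 80%. The documents do not say that. It is what follows if the model sentence and the ROC sentence are read together, and the figure is conditional on that reading.

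The reply does not remove the point. No locked rule is written down, and the Background also speaks of the assay as being developed. Nor may a reader infer that locking the score is enough. The step that makes a locked score plausible, step 10, is also the one that lets the assay choose which foods acquire labels. Whether those outcomes enter the ROC is not stated either, so the 3–58% is conditional too.

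A further objection is that leave-one-child-out with the ordinary clustered interval may be good enough, since one set of simulations put it at 3.7–6.2%. Another gave 6–11%. A permutation null is supported as better calibrated, but it is not the only acceptable method.

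**Conclusion.** The concern holds in conditional form and should be fixed before analysis. The rule cannot be interpreted until both the score and the label set are named. On the natural reading, a useless assay is called predictive in roughly 83–94% of trials, and more often if the child's random effect enters the score. That figure barely moves over 8–40 foods, 10–20 children and correlation 0–0.6. For a locked score with labels independent of the assay, the rule behaves about as intended (2–5%). For a locked score with assay-selected foods, the rate runs from about 3% to 58% and depends heavily on the assumed numbers of known-safe and unknown foods.

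Confidence is high for the in-sample result, which a closed-form calculation and separate simulations agree on. It is lower for the exact size of the selection effect. None of this is evidence that the assay fails to work.

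**What to change.** 1. **Labels.** State that the primary ROC uses foods whose safe or trigger status was established independently of the assay result, for example documented history at the blood draw. Report foods introduced on the assay's advice separately.
2. **Locked score.** If the score is fixed before these data, give its formula and keep the 0.5 rule for that label set.
3. **Fitted score.** If the score comes from the logit, base the decision on leave-one-child-out predictions: refit on the other children, score the held-out child from the fixed biomarker coefficients only, and repeat any biomarker selection in each fold. Report the in-sample AUC as descriptive. Judge the out-of-sample AUC by a method with a stated false-positive rate. One choice is a permutation null that shuffles labels among each child's own foods and repeats every refit, with one-sided p at most 0.025. Its exchangeability assumption depends on item 1. State the expected numbers of children and classified foods and the resulting power.

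**Cost.** A few sentences and no new data. Under item 3, 999 permutations × 20 folds is about 20,000 small refits, an estimated 2–3 minutes; that version was not itself simulated. The reported AUC will be lower: at true AUC 0.70, 0.68 instead of 0.73 in-sample with 20 × 20, and 0.64 instead of 0.76 with 10 × 10. Power falls if enrolment or classified foods fall short, and restricting the label set reduces classified foods. A locked score keeps more power at AUC 0.70 (100%, 100%, 97% and 94% in the order of the power table), but that is a best case using the true weights.
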